4.1.1 China and Japan sub-population

The China and Japan sub-populations are defined as all patients enrolled in sites in China (including mainland and Taiwan) and Japan, respectively.

To support registration in China and Japan, study summaries will be repeated for the China and Japan sub-populations, which includes but may not be limited to patient disposition, demographic and baseline characteristics, extent of exposure, prior and concomitant medications, efficacy, and safety analyses. Results in the China and Japan sub-populations may be reported separately with the objective of demonstrating consistency with the overall population.

Efficacy analyses in the China and Japan sub-population will proceed as described in Section 4.2.5, Section 4.2.6, and Section 4.2.7. Additional consideration should be given in case of a limited number of event(s) in a regional sub-population. Specifically, time to event analysis using Cox regression will not be conducted in case of < 10 events. Responder analysis using logistic regression will include only treatment group as model covariate in case of < 10 responders. Similarly, unadjusted estimate from negative binomial regression will be provided in case of < 10% subjects with event(s). If event number in either treatment group is 0 in a stratum, results from unstratified Cochran–Mantel–Haenszel analysis will be reported.

Exploratory and supplementary/sensitivity analyses may be replicated for the China and Japan sub-population, if deemed informative. All analyses based on the China and Japan sub-population will be considered exploratory. No adjustment for multiplicity will be made; thus the testing strategy detailed in 4.1.3 will not be employed directly to the China and Japan sub-population.

Safety analyses will include summaries of AE overview, AEs, and SAEs by System Organ Class (SOC) and Preferred Term (PT). Descriptive summary of PK concentrations will be repeated as well for the China and Japan sub-population.

The analyses for regional registration in China and Japan will be presented separately from the global CSR.

4.1.2 Hypothesis tests for co-primary endpoints

The co-primary efficacy endpoints are the change from baseline in total NPS at Week 56 and the change from baseline in bi-weekly mean NBS at Week 56. The primary analysis is to compare the changes from baseline in total NPS and in NBS of benralizumab with placebo. The following hypothesis will be tested for the co-primary endpoints:

- H_0 : The change from baseline in total NPS and/or the change from baseline in NBS are similar between benralizumab and placebo.

- H_1 : Both of the change from baseline in total NPS and the change from baseline in NBS are different between benralizumab and placebo.

The co-primary endpoints will be evaluated using a hybrid method of the worst-possible/worst-observation carried forward and multiple imputation, followed by an analysis of covariance with treatment arm, baseline scores of corresponding endpoint, region, CCI as covariates.

4.1.3 Method for multiplicity control

To account for multiplicity to test the co-primary endpoints (change from baseline in total NPS at Week 56 and change from baseline in bi-weekly mean NBS at Week 56) and the three key secondary endpoints (the change from baseline in bi-weekly mean DSS, LMS, and SNOT-22 total score at Week 56), the type I error will be controlled across co-primary and key secondary endpoints at 0.05 (two-sided) statistical significance level. Both of the co-primary and the key secondary endpoints will be tested at 0.05 (two-sided) level. A testing strategy below will be as follows.

- Step 1: Perform the 2 tests of co-primary endpoints at a significant level of 0.05. If both p-values are less than 0.05, then proceed to Step 2. Otherwise no null hypothesis is rejected.
- Step 2: Test the three key secondary endpoints using a step-down approach following the hierarchical order: bi-weekly mean DSS, LMS, and SNOT-22 total score for at the significant level of 0.05. If at any time a null hypothesis cannot be rejected in favour of the benralizumab group, further testing will stop, and no subsequent null hypotheses in the testing hierarchy will be rejected.

4.1.4 Description of estimands used in the analyses

4.1.4.1 Primary estimand

The primary estimand quantifies the difference in outcomes for patients randomised to the benralizumab and placebo arms at the planned timepoints of the study, regardless of the treatment that patients actually received, where rescue by surgery and/or SCS use for CRSwNP indicates failure.

An ANCOVA model will be used with treatment arm, baseline score (for the respective endpoint), region, CCI as covariates. Handling strategy of intercurrent events are specified as follows:

- *Nasal polyp surgery*: a nasal polyp surgery is considered as treatment failure. The composite strategy will be applied where the worst possible (WP) score for the respective endpoint will be used for post-surgery assessments.
- *SCS use for CRSwNP*: SCS use for CRSwNP is considered as treatment failure but less severe than surgery. The composite strategy will be applied where the worst

observation prior to the SCS use will be carried forward (WO CF) for post-SCS assessments.

- *Treatment discontinuation*: the treatment policy strategy will be applied.

The analysis includes all the data collected during the study including data collected after discontinuation of study treatment except data collected after surgery and/or SCS use for CRSwNP. For participants who discontinue the study without any rescue event (i.e. NP surgery and/or SCS use for CRSwNP), a multiple imputation (MI) approach will be used to impute missing values assuming missing at random (MAR). The estimates of treatment effects will be based on contrasts from the ANCOVA model.

A supplementary analysis will use a different strategy (treatment policy strategy) for SCS use for CRSwNP. In this supplementary analysis, a composite strategy will be used only for patients who undergo surgery for CRSwNP in which data collected post-surgery will be set to missing, and the patient's worst possible value will be imputed from that point through Week 56. For patients who discontinue the study without surgery, missing data will be imputed using a multiple imputation using all patients who did not have surgery. Patients who receive SCS for CRSwNP without having surgery for CRSwNP will be included in non-surgery patients. Details of this supplementary analysis are included in Appendix 8.2.

4.1.4.2 Effectiveness estimand

The effectiveness estimand quantifies the difference in outcomes for patients randomised to the study treatment and control arms, while on treatment and without having been rescued by surgery and/or SCS use for CRSwNP, at the planned endpoint of the study. In the effectiveness estimand, while-on-treatment strategy will be applied for all intercurrent events, and all the data up to the IP discontinuation visit will be included except the data observed after surgery and SCS use for CRSwNP. No imputation will be conducted for missing data as analysis will use an ANCOVA model for repeated measures. A supplementary analysis will be evaluated under the effectiveness estimand. Details of the supplementary analyses are included in Appendix 8.4.

4.1.4.3 Treatment policy estimand

The treatment policy estimand quantifies the difference in outcomes for patients randomised to the study treatment and control arms at the planned endpoint of the study, regardless of the occurrence of intercurrent events. The treatment policy estimand includes all the data collected during DB period including data collected after discontinuation of study treatment, surgery for CRSwNP, or SCS use for CRSwNP. No imputation will be conducted for the missing data as analysis will use an ANCOVA model for repeated measures. A supplementary analysis will be evaluated under the treatment policy estimand. Details of this supplementary analysis are included in Appendix 8.5.

4.1.5 Sensitivity analyses for missing data

Sensitivity analyses of the ANCOVA with missing data imputed will be performed for co-primary endpoints (and key secondary endpoints when specified) using controlled sequential

multiple imputation (MI) methods based on pattern mixture models, as described in the CHMP Guideline on Missing Data in Confirmatory Clinical Trials (CHMP 2010) and by Little et al (Little et al 2010). Details are included in Appendix 8.3.

4.2 Analysis methods

4.2.1 Patient disposition

Patient disposition will be summarised using the All Patients Analysis Set. The total number of patients will be summarised for the following groups: those who enrolled and those who were not randomised (and reason). The number and percentage of patients within each treatment group will be presented by the following categories: randomised, received treatment with study drug, did not receive treatment with study drug (and reason), completed treatment with study drug in DB period, discontinued treatment with study drug in DB period (and reason), discontinued treatment with study drug in DB period but completed DB follow-up, completed DB period, and withdrew from DB period (and reason).

For patients who completed the DB period, the number and percentage of patients will be presented by the following categories in the OLE analysis set: enrolled in the OLE period, completed treatment in OLE period, discontinued treatment in OLE period (and reason), completed OLE period, and withdrew from OLE period (and reason).

Screen failure information will be listed for the All Patients Analysis Set.

The number of patients randomised by country and centre will be summarised by treatment group for patients in the PFAS.

4.2.2 Demographics and baseline characteristics

The demographics and key subject baseline variables (Section 3.2) will be descriptively summarised based on FAS and PFAS. This summary will be repeated for the OLE period using the OLE analysis set.

CRSwNP and respiratory disease characteristics (Section 3.2) and asthma disease characteristics (Section 3.2) at baseline will be descriptively summarised based on PFAS.

4.2.3 Prior and concomitant medications

The number and percentage of patients who take maintenance medications will be summarised.

The number and percentage of patients who take prior medications and patients who take allowed concomitant medications will be summarised over the DB period based on FAS, and patients who take disallowed concomitant medications will be based on the PFAS; these may be repeated over the OLE period based on the OLE analysis set. Concomitant medications

will be classified according to the WHODRUG dictionary. The summary tables will present data by generic term within Anatomical Therapeutic Chemical (ATC) code.

4.2.4 Study treatment administration

4.2.4.1 Exposure

Duration of the study drug exposure over the DB period and the OLE period will be summarised by treatment group for the safety analysis set and OLE analysis set, respectively. Duration of IP administration will be calculated in days as:

Duration of IP administration in the DB period = Date of last dose or early discontinuation in the DB – Date of first IP dose in the DB + 1.

Duration of IP administration in the OLE period = Date of last dose or early discontinuation in the OLE – Date of first IP dose in the OLE + 1.

4.2.4.2 Study treatment compliance

Study treatment compliance during the DB period and during the OLE period will be summarised by treatment group for the patients in the PFAS and OLE analysis set, respectively. In addition, compliance during the on-study period may be summarised using the PFAS. Study treatment compliance during the DB period will be reported at the primary DBL, and compliance during the OLE (and on-study) period will be reported at the final DBL.

Compliance will be calculated as:

Study treatment compliance = (total doses administered / total doses expected) x 100%.

Total number of doses expected includes all visits with protocol scheduled IP administration on or before a patient's IP discontinuation or treatment completion date during DB period (where the last IP is dosed at Week 48), OLE period (where the first IP starts at Week 56), and on-study, respectively.

4.2.5 Primary efficacy variables: nasal polyps score and nasal blockage score

Co-primary efficacy endpoints will be collected during the double blinded period according to the SoA Table 2 in the CSP. No data from the OLE period will be collected for co-primary endpoints. Therefore following analyses specified in Section 4.2.5.1 to 4.2.5.4 only apply to the double blind period at the primary DBL.

The co-primary efficacy endpoints are the change from baseline in total NPS at Week 56 and the change from baseline in bi-weekly mean NBS at Week 56.

The efficacy endpoints will be summarised by treatment and time point (i.e. week number) during DB period for all patients in PFAS.

4.2.5.1 Primary analysis

The primary analysis for both co-primary endpoints will use the primary estimand as described in Section 4.1.4.1. An ANCOVA model will be conducted adjusting for treatment arm, baseline scores (baseline total NPS for NPS model and baseline bi-weekly mean NBS for NBS model), region, CCI as covariates. Estimates of the treatment effects at Week 56 were based on contrasts from the ANCOVA model. The analysis includes all patients with baseline and at least one evaluable post-baseline assessment and all the patients with a baseline assessment who are rescued by surgery and/or SCS use for CRSwNP. For participants who discontinue the study without any rescue event (i.e. NP surgery and/or SCS use for CRSwNP), a multiple imputation (MI) approach will be used to impute missing values assuming missing at random (MAR).

Specifically, if a patient has surgery or SCS use for CRSwNP before Week 56, the data will be censored after the time of the first surgery and/or the time of having the first course of SCS use for CRSwNP, and the patient's worst-possible/previously worst-observed value will be imputed in its place. For patients rescued by SCS use for CRSwNP whose post-baseline values are all missing or for whom every post-baseline value is after rescue by SCS use for CRSwNP, the baseline will be used to impute. If a patient has surgery for CRSwNP before Week 56, the data will be censored after the time of the first surgery for CRSwNP and the worst possible value will be imputed in its place. If there is sufficient evaluable NBS data prior to rescue in the bi-weekly period in which rescue occurs, the bi-weekly mean for that period will be based on the data collected prior to rescue. Otherwise, the WP/WOCF will be imputed for that period as well. See Table 13 for a full list of WP values. For patients who discontinue the study without surgery or SCS use for CRSwNP, missing data will be imputed using multiple imputation using all patients who does not have surgery or receive SCS use for CRSwNP.

The following 5 steps will be used to build the imputation datasets and perform analyses:

1. 100 datasets with a monotone missing pattern will be obtained, induced by Markov Chain Monte Carlo (MCMC) method on all patients with at least one post-baseline and pre-rescue (if applicable) evaluable assessment (utilizing only data prior to surgery and/or SCS use for CRSwNP, or Week 56, whichever comes first for those rescued). The model for MCMC imputation will include adjustment for covariates including treatment group, region, CCI and baseline value of the response value. See Table 14 for random seeds to be used for MCMC step.
2. For each of the imputed datasets obtained in step 1, the remaining missing data for patients who are not rescued by surgery or SCS for CRSwNP by the end of double blind period will be imputed using the regression method for the monotone pattern with adjustment for covariates including treatment groups, region, CCI and baseline value of the response variable. No data from rescued patients is included in this step. See Table 14 for random seeds to be used for monotone regression step.

3. For patients who are rescued by surgery or SCS for CRSwNP by the end of double blind period, any remaining missing data following step 1 after the time of surgery or SCS use for CRSwNP will be replaced by the WP/WOCF approach described above. Any missing data between the last observed value and the date of rescue (for those patients that are rescued by Week 56) will be replaced using last observation carried forward (LOCF). Similarly for patients with only a baseline prior to rescue (who are excluded from step 1), any missing data after rescue will be replaced by WP/WOCF and any missing data between baseline and rescue will be replaced with the baseline value (baseline LOCF). This approach ensures complete data for all patients at all timepoints without forcing a poor outcome (i.e. WP/WOCF) prior to rescue.
4. For each of the 100 imputations, the datasets from the rescued and non-rescued patients will be combined to create 100 complete datasets which will then be analysed using the main statistical model. These 100 datasets will be saved.
5. Apply Rubin's rule to combine analysis results (point estimates and standard errors) from 100 imputations. The estimated least squares (LS) means, difference in LS means, and the corresponding 95% confidence intervals (CI) will be provided along with the nominal p-values for Week 56 and all earlier time points in turn.

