9.4.1. Efficacy analyses

All analyses described below apply to the primary full analysis set (PFAS), through to IPD/EoDB (Week 56) unless otherwise stated. The primary database lock will occur after all randomised patients have been followed up for the 56-week double-blind treatment period. The study will remain blinded until the primary database lock. The final database lock will occur after the last patient completes the OLE. All available data captured during the DB period and selected safety data from the OLE period will be reported at the primary DBL, while remaining data from the OLE period will be reported separately at the final DBL. Unblinding and data analysis will occur after the primary database lock.

The primary estimand for co-primary endpoints will quantify the difference in change from baseline between patients randomized to benralizumab and placebo at the planned timepoints, regardless of the treatments that patients actually received, where rescue by CRSwNP surgery and/or SCS_NP indicates failure. It includes all the data collected during the study including data collected after discontinuation of study treatment except data collected after CRSwNP surgery and/or SCS_NP. A composite strategy will be used for patients who undergo CRSwNP surgery or receive SCS for CRSwNP. Data collected post-SCS_NP will be set to missing, and the patient's worst observed post-baseline value on or before the time of SCS_NP will be imputed from that point through Week 56. Data collected post-surgery will be set to missing, and the worst possible value will be imputed from that point through Week

56. For patients who discontinue the study without surgery or SCS_NP, missing data will be imputed using multiple imputation using all patients who did not have surgery or receive SCS_NP. Details of the primary analysis as well as sensitivity analyses will be included in the SAP.

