3.1.2 Visit window definitions

For endpoints that present visit-based data, the variables will be summarised based on the scheduled days with adjusted analysis-defined visit windows. The adjusted analysis-defined visit windows will be based on the collection schedule listed in the protocol and variables will be windowed to the closest scheduled visit for those variables.

Visit windows have been constructed so that every observation collected can be allocated to a particular visit. However, all values will be included in data listings. Of note, Day 1 indicates the beginning of analysis periods following the Clinical Data Interchange Standards Consortium (CDISC) standards, although it is labelled as Day 0 in the CSP.

For each analysis parameter, the windowing will be based on the protocol-specified schedule of events as defined in Table 1, Table 2, and Table 3 of the CSP. If multiple readings are recorded within a single visit window, the following rules will apply:

- If there are 2 or more valid, non-missing observations within the same visit window, then the non-missing one which is closest to the scheduled visit day will be used in the analysis.
- If 2 valid observations are equidistant from the scheduled visit, then the non-missing observation with the earlier collection date will be used in the analysis for the post-baseline observations and the non-missing observation with the later collection date will be used in the analysis for the screening observations.
- If 2 or more valid observations are collected on the same day after Day 1, then the non-missing observation with the earlier collection time will be included in the

analysis. And the non-missing observation with the later collection time will be included in the analysis if these records were collected during the screening.

- If 2 non-missing values (for continuous variables) are recorded on the same day and have no assessment time associated with at least one of them, or the same assessment time associated with both of them, the average of the two values will be selected for analysis at that visit. For categorical variables in this situation, the worst case will be used.

If a visit window does not contain any observations, then the data will remain missing.

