For assignment of data to adjusted analysis-defined visit windows, study day will be calculated relative to the reference start date, which is the date of randomization for efficacy variables and the date of first dose of study treatment for safety variables.

- Screening period: $Study\ day = Date\ of\ assessment - reference\ start\ date$
- After randomisation: $Study\ day = (Date\ of\ assessment - reference\ start\ date) + 1$

The adjusted analysis-defined windows for NPS are defined as in [Table 3](#) below:

Table 3 Adjusted analysis-defined visit windows for NPS

Analysis-defined visit windows	Scheduled study day	Maximum windows
Week -6	-42	$-49 \leq Study\ day \leq -15$
Week -2	-14	$-14 \leq Study\ day \leq 1$
Week 8	57	$2 \leq Study\ day \leq 84$
Week 16	113	$85 \leq Study\ day \leq 140$
Week 24	169	$141 \leq Study\ day \leq 224$
Week 40	281	$225 \leq Study\ day \leq 336$
Week 56	393	$337 \leq Study\ day \leq \min(434, \text{first OLE dose})$; first OLE dose is applicable for those who entered the OLE after DB completion

The NBS, DSS, Total Symptom Score (TSS), and other items in the nasal symptom scores diary (NPSD) will be summarised every two weeks (bi-weekly) and the adjusted windows are defined as in [Table 4](#) below.

Table 4 Adjusted analysis-defined visit windows for NPSD (including NBS, DSS, and TSS)

Analysis-defined visit windows	Scheduled study day	Maximum windows
Week 1, Day 1	1	$-13 \leq Study\ day \leq 1$
Week 2	15	$2 \leq Study\ day \leq 15$
Week 4	29	$16 \leq Study\ day \leq 29$
Week 6	43	$30 \leq Study\ day \leq 43$

...
Week 56	393	$380 \leq \text{Study day} \leq \min(393, \text{first OLE dose})$; first OLE dose is applicable for those who entered the OLE after DB completion

The general adjusted analysis-defined windows for the visits following baseline for all other assessments in Table 2 and Table 3 of the CSP is summarised in Table 5. The windowing will only be performed for assessments within the appropriate periods, e.g. double-blind versus open label.

Table 5 General analysis-defined visit windows for assessments

Analysis-defined visit windows	Scheduled study day	Maximum windows
Week 1 Day 1	1	Study day=1
Week X	$X*7+1=a$	$2 \leq \text{Study day} \leq ((b-a)/2+a)-1$
Week Y ^a	$Y*7+1=b$	$((b-a)/2+a) \leq \text{Study day} \leq ((c-b)/2+b)-1$
Week Z	$Z*7+1=c$	$((c-b)/2+b) \leq \text{Study day}$

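### For NPS and SNOT-22, the SAP does not ensure that a patient rescued shortly before Week 56 is scored as a failure at Week 56

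*SAP*

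**What the plan says.** **Intent.** Protocol 9.4.1 states "Data collected post-surgery will be set to missing" and imputes the worst possible value from surgery through Week 56. After SCS for CRSwNP, the worst observed post-baseline value is carried to the same point. SAP 8.3 describes imputation until Week 56, and SAP 4.1.4.1 defines rescue as failure.

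**Algorithm.** SAP 4.2.5.1 gives the surgery rule as "If a patient has surgery for CRSwNP before Week 56, the data will be censored after the time of the first surgery for CRSwNP", with WP imputed in place of what was censored. Step 1 builds the imputation data "utilizing only data prior to surgery and/or SCS use for CRSwNP, or Week 56, whichever comes first for those rescued". Step 3 then says "any remaining missing data following step 1 after the time of surgery or SCS use for CRSwNP will be replaced by the WP/WOCF approach".

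**Windowing.** SAP 3.1.2 allocates every observation to a visit. Where a window holds several values, "the non-missing one which is closest to the scheduled visit day will be used in the analysis"; if two are equally distant, "the non-missing observation with the earlier collection date will be used in the analysis for the post-baseline observations". The rescue date plays no part. Table 3 runs the Week 56 NPS window from Day 337 to Day 434 or the first OLE dose, around a scheduled Day 393.

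**Pre-rescue assessments.** Protocol 8.1.4 (surgery) and 8.1.5 (SCS) each call for an NPS and a SNOT-22 before rescue.

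**The concern.** A pre-rescue NPS or SNOT-22 taken late in the double-blind period can lie inside the Week 56 window. If it is selected, the Week 56 cell is not missing, and step 3 has nothing to replace. The patient has had surgery before Week 56 but carries the pre-surgery score into the ANCOVA.

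Two programmers following the SAP could also give the same patient different values, because the order of censoring and windowing is not stated. This affects a co-primary endpoint and a key secondary endpoint at the multiplicity-protected timepoint. It would be awkward to settle after unblinding.

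The responder rule in SAP 3.1.5 shows the missing element: anyone rescued by the timepoint is a non-responder, whatever was observed. One patient could therefore be a Week 56 NPS non-responder and still have an unpenalised Week 56 NPS in the primary analysis.

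**Working it through.** **1. The plan's own power figure.** Inputs from SAP 1.4: 125 per arm, SD 2 (NPS) and 1 (NBS), differences 0.85 and 0.4, two-sided t-test at 0.05. Noncentral t gives 0.917 for NPS and 0.883 for NBS. If the two are independent, joint power is 0.917 × 0.883 = 0.810, consistent with the stated overall 80%. The critical differences are 1.97 × 2 × √(2/125) = 0.498 and half that, 0.249, matching 0.50 and 0.25.

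**2. Windows.** The start is the midpoint of adjacent scheduled days.
- NPS: (281 + 393)/2 = Day 337, as in Table 3.
- SNOT-22 by the Table 5 formula: (337 + 393)/2 = Day 365, if Week 48 is the preceding assessment.

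**3. The rules applied to hypothetical patients.** WP is 8 for NPS and 110 for SNOT-22 (SAP Table 13).

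| Case | Week 56 value, windowing first | Week 56 value, censoring first |
|---|---|---|
| NPS 6 on Day 358, surgery Day 360, V11 Day 393 | 8 | 6 |
| Same, V11 missed | 6 | 6 |
| NPS 6 on Day 386, then surgery, V11 Day 400 | 6 | 6 |
| SNOT-22 50 on Day 373, surgery Day 375, V11 Day 393 | 110 | 50 |
| Same, V11 missed | 50 | 50 |

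In the third row the distances tie (393 − 386 = 7 and 400 − 393 = 7), and the earlier date wins. In general, with V11 on Day 393 + d (d up to 7 within the visit window), a pre-rescue value from Day 393 − d onward is selected; for d = 3 that is Day 390.

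**4. Size per patient.** One net affected surgery patient on placebo shrinks the NPS difference by (8 − pre-surgery NPS)/125:
- NPS 7: 1/125 = 0.008 (0.9% of 0.85)
- NPS 6: 2/125 = 0.016 (1.9%)
- NPS 5: 3/125 = 0.024 (2.8%)

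For SNOT-22, assumed pre-surgery scores of 70 and 50 give 40/125 = 0.32 and 60/125 = 0.48 points.

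**5. How many patients (assumptions).** The documents give no rescue rates or timing. Only rescue in the last 8 weeks matters for NPS.
- Low case: surgery in 10% against 8%, evenly over 56 weeks: 125 × 0.02 × 8/56 = 0.4 net patients.
- High case: 15% against 5.5%, with none in the first 13 weeks: 125 × 0.095 × 8/43 = 2.2. This overcounts, because it takes every surgery in the last 8 weeks as affected, and some pre-surgery visits will fall before Day 337.

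**6. Effect on power** (SD held at 2, 2-point gap):

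| Net patients | Shift | NPS power | Joint, independent |
|---|---|---|---|
| 0 | 0 | 0.917 | 0.810 |
| 0.4 | 0.006 | 0.913 | 0.806 |
| 1 | 0.016 | 0.907 | 0.801 |
| 2 | 0.032 | 0.896 | 0.791 |

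One patient with a 3-point gap (shift 0.024) gives a joint power of 0.796. With a correlation of 0.3 or 0.5 between the co-primaries, the two-patient case gives about 0.804 or 0.816. Fewer imputed 8s would also lower the SD, so the loss is if anything overstated.

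**The case against.** The best defence is that the rule is already stated. SAP 4.1 and 4.1.4.1 use WP for assessments after surgery, and step 3 refers back to that approach. Week 56 follows any surgery that precedes it, so a sensible programmer would impute WP. Windowing first is at least as natural an order, since the imputation runs on visit-indexed data, and with V11 done near Day 393 it gives the intended 8. Step 3 also says that it avoids forcing a poor outcome before rescue, and the effect is small.

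Much of this stands. The intent is clear, the censoring-first route is an inference, and the size is modest. But the general rule replaces only what was censored after surgery. It does not say that WP displaces an earlier value already occupying the window. With V11 missed, or late and no closer to Day 393, the wrong value results under either order. Avoiding a poor outcome before rescue is right for earlier visits, but does not justify a pre-rescue score at Week 56 for a patient already rescued.

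Two stronger readings should be resisted.
- A reader might infer from the LMS supplementary analysis (SAP 4.2.6.2) that the sponsor wrote this very override for CT and left it out for NPS. That text concerns patients given SCS before the scan, so the observed value it replaces is a post-SCS one. It is not a precedent.
- A reader might see the NBS rule, under which "the bi-weekly mean for that period will be based on the data collected prior to rescue", as the same defect. It is explicit and deliberate, uses no post-rescue data, and matters only for rescue in the last days of the final diary period. It needs no change.

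**Conclusion.** The point holds for NPS and SNOT-22. As written, windowing plus replacement of missing data only can leave a pre-rescue score as the Week 56 value, contrary to Protocol 9.4.1, SAP 8.3 and the primary estimand. It is confined to rescue inside the Week 56 window with a pre-rescue assessment also in that window; patients rescued earlier receive WP/WOCF at Week 56.

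The effect is probably small: 0.008 to 0.024 NPS points per net affected surgery patient, with perhaps 0.4 to 2 net patients under assumed rates. For SCS it is smaller, and nil when the pre-SCS value is already the worst observed after baseline. Joint power slips just below 80% only if the shift reaches about 0.02 and the co-primaries are close to independent.

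A reader might infer a bias in favour of benralizumab or an inflated type I error. The documents do not support that. The direction depends on which arm has more late rescues, and if that is placebo the treatment difference shrinks. Nor has the estimand been changed: the stated intent is right and the algorithm does not enforce it. The correction is worth making because it settles a co-primary value in advance at almost no cost.

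**What to change.** Add to SAP 4.2.5.1, before unblinding:

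> For NPS and SNOT-22, if the first surgery or SCS course for CRSwNP starts before the V11 assessment (or, if V11 is not done, before Day 393), the Week 56 value is set to WP/WOCF whether or not a pre-rescue value lies in the Week 56 window. Such a pre-rescue value is used only to determine the worst observed value. A V11 assessment made before rescue on the same day is kept.

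The last sentence protects a valid Week 56 endoscopy followed by same-day SCS, the sequence Protocol 8.1.5 asks for. The Day 393 limit keeps rescue after the scheduled Week 56 day from counting when V11 is absent. With this rule the order of censoring and windowing no longer affects Week 56.

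The cost is three sentences and one programming condition. It needs no new data and does not change the estimand. The NBS and DSS handling stays as it is.
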